11.1 Toxicity Scale

All AEs that occur during the study should be assessed according to the DAIDS Table for Grading the Severity of Adult and Pediatric Adverse Events (DAIDS AE Grading Table), Version 2.0 (November, 2014).

Some grade 1 laboratory parameters on the DAIDS Toxicity Table fall within the NIH lab reference range for normal values. These normal values will not be reported as grade 1 adverse events.

11.1.1 Causality

Causality (likelihood that the event is related to the study agent) will be assessed considering the factors listed under the following categories:

Definitely Related:

- Reasonable temporal relationship
- Follows a known response pattern
- Clear evidence to suggest a causal relationship
- There is no alternative etiology

Probably Related:

- Reasonable temporal relationship
- Follows a suspected response pattern (based on similar agents)
- No evidence of a more likely alternative etiology

Possibly Related:

- Reasonable temporal relationship
- Little evidence for a more likely alternative etiology

Unlikely Related:

- Does not have a reasonable temporal relationship
OR
- Good evidence for a more likely alternative etiology

Not Related:

- Does not have a temporal relationship
OR
- Definitely due to an alternative etiology

Note:

Causality assessment is based on available information at the time of the assessment of the AE. The Investigator may revise the causality assessment as additional information becomes available.

11.2 Recording/Documentation

At each contact with the subject, information regarding AEs will be elicited by appropriate questioning and examinations and will be immediately recorded on a source document. Source documents will include: progress notes, laboratory reports, consult notes, phone call summaries, survey tools, and data collection tools. Source documents will be reviewed in a timely manner by the research team. All reportable AEs that are identified will be recorded in CRIMSON. The start date, the stop date, the severity of each reportable event, and the PI's judgment of the AEs relationship to the study agent/intervention will also be recorded in CRIMSON.

11.3 Definitions

Adverse Event (AE): Any untoward or unfavorable medical occurrence in a human subject, that includes any abnormal sign (e.g. abnormal physical exam or laboratory finding), symptom, or disease, temporally associated with the subject's participation in the research, whether or not considered related to the research.

Adverse Reaction (AR): An adverse event that is caused by an investigational agent (drug or biologic).

Suspected Adverse Reaction (SAR): An adverse event for which there is a reasonable possibility that the investigational agent caused the adverse event. 'Reasonable possibility' means that there is evidence to suggest a causal relationship between the drug and the adverse event. A suspected adverse reaction implies a lesser degree of certainty about causality than an adverse reaction, which implies a higher degree of certainty.

Serious adverse event (SAE): Any adverse event that results in one or more of the following outcomes:

- Death
- Life-threatening (i.e. an immediate threat to life) event
- Inpatient hospitalization or prolongation of existing hospitalization
- Persistent or significant incapacity or substantial disruption of the ability to conduct normal life functions
- Congenital anomaly/birth defect
- Medically important event*

*Medical and scientific judgment should be exercised in deciding whether expedited reporting is appropriate in other situations, such as important medical events that may not be immediately life threatening or result in death or hospitalization, but may jeopardize the subject or may require intervention to prevent one of the other outcomes listed above.

Unexpected Adverse Event: An AE is unexpected if it is not listed in the Investigator's Brochure or Package Insert (for marketed products) or is not listed at the specificity or severity that has been observed. It is the responsibility of the IND Sponsor to make this determination.

Serious and Unexpected Suspected Adverse Reaction (SUSAR): A SUSAR is a suspected adverse reaction that is both serious and unexpected.

Unanticipated Problem (UP): Any incident, experience, or outcome that is:

1. Unexpected in terms of nature, severity, or frequency in relation to
 - a. The research risks that are described in the IRB-approved research protocol, informed consent document, Investigator's Brochure, or other study documents; and
 - b. The characteristics of the subject population being studied; and
2. Possibly, probably, or definitely related to participation in the research; and
3. Places subjects or others at a greater risk of harm (including physical, psychological, economic, or social harm) than was previously known or recognized. (Per the IND Sponsor, an AE with a serious outcome will be considered increased risk.)

Unanticipated Problem that is not an Adverse Event (UPnonAE): An unanticipated problem that does not fit the definition of an adverse event, but which may, in the opinion of the Investigator, involve risk to the subject, affect others in the research study, or significantly impact the integrity of research data.

Protocol Deviation: Any change, divergence, or departure from the IRB-approved study procedures in a research protocol. Protocol deviations are designated serious or non-serious and further characterized as:

1. Those that occur because a member of the research team deviates from the protocol
2. Those that are identified before they occur, but cannot be prevented
3. Those that are discovered after they occur

Serious Protocol Deviation: A deviation that meets the definition of a SAE or compromises the safety, welfare, or rights of subjects or others.

Non-Compliance: The failure to comply with applicable NIH HRPP policies, IRB requirements, or regulatory requirements for the protection of human subjects. Non-compliance is further characterized as:

1. Serious: Non-compliance that:
 - a. Increases risks or causes harm to participants
 - b. Decreases potential benefits to participants
 - c. Compromises the integrity of the NIH-HRPP
 - d. Invalidates the study data
2. Continuing: Non-compliance that is recurring
3. Minor: Non-compliance that is neither serious nor continuing

11.4 Adverse Event Reporting

11.4.1 Expedited Reporting to the NIAID IRB

Unanticipated problems that are either AEs or non-AEs (as defined by Section 11.3) and Serious Protocol Deviations will be reported within seven calendar days of Investigator awareness. Serious Adverse Events that are possibly, probably, or definitely related to the research will be

reported to the NIAID IRB within seven calendar days of Investigator's awareness, regardless of expectedness.

11.4.2 Annual Reporting to the NIAID IRB

The following items will be reported to the NIAID IRB in summary at the time of Continuing Review:

- Serious and non-serious unanticipated problems
- SAEs that are possibly, probably, or definitely related to the research
- SAEs that are not related to the research
- All AEs.
- Serious and Non-Serious Protocol deviations
- Serious, continuing, and minor non-compliance
- Any trend or event that, in the opinion of the Investigator, should be reported

11.4.3 Investigator Reporting Responsibilities to the Sponsor

Adverse Events: Line listings, frequency tables, and other summary AE data will be submitted to the IND Sponsor when needed for periodic safety assessments, review of IND annual reports, review of IND safety reports, and in the preparation of final study reports.

SAEs (whether or not they are also UPs) must be reported on the Safety Expedited Report Form (SERF) and sent to the Sponsor Clinical Safety Office (CSO) by fax or e-mail attachment.

Deaths and immediately life threatening SAEs must be reported within one business day after the site becomes aware of the event. All other SAEs must be reported within three business days of site awareness.

SPONSOR CLINICAL SAFETY OFFICE CONTACT INFORMATION:

OCRPRO Clinical Safety Office
[name]
[name]

[contact]
[contact]
E-mail: [contact]

Non-Serious AEs that are UPs must also be reported on the SERF and sent to the CSO by fax or e-mail attachment no later than seven calendar days of site awareness of the event. The UPs that are not AEs are not reported to the Sponsor CSO.

Pregnancy: Although pregnancy itself is not an AE, events that meet SAE criteria during pregnancy, delivery, or in the neonate (e.g., congenital anomaly/birth defect) are reportable on the SERF. Pregnancy and pregnancy outcome data (e.g. delivery outcome, spontaneous or elective termination of the pregnancy) will be reported to the CSO within three business days of the site's awareness via email or fax.

11.5 FOLLOW-UP OF ADVERSE EVENTS AND SERIOUS ADVERSE EVENTS

AEs that occur following enrollment of the subject (by signing the informed consent) are followed until the final outcome is known or until the end of the study follow-up period.

SAEs that have not resolved by the end of the follow-up period are followed until the final outcome is known. If it is not possible to obtain the final outcome for an SAE (e.g. the subject is lost to follow-up), the reason that a final outcome could not be obtained will be recorded by the Investigator on the AE case report form (CRF), if the CRF is still open, and the SERF as applicable.

SAEs that occur after the study follow-up period that are reported to the Investigator and are assessed to be possibly, probably, or definitely related to the study agent must be reported to the CSO, as described above.

11.6 Sponsor's Reporting Responsibilities

Serious, unexpected, suspected adverse reactions (SUSARs) as defined in 21 CFR 312.32 will be reported to FDA and all participating Investigators as IND Safety Reports. The sponsor will also submit a brief report of the progress of the investigation to the FDA on an annual basis as defined in 21 CFR 312.33.

12 CLINICAL MONITORING STRUCTURE

12.1 Site Monitoring Plan

As per ICH-GCP 5.18 and FDA 21 CFR 312.50, clinical protocols are required to be adequately monitored by the study sponsor. Study monitoring will be conducted according to the "NIAID Intramural Clinical Monitoring Guidelines". Monitors under contract to the NIAID/OCRPRO will visit the clinical research site to monitor aspects of the study in accordance with the appropriate regulations and the approved protocol. The objectives of a monitoring visit will be:

- 1) To verify the existence of signed informed consent documents and documentation of the ICF process for each monitored subject;
- 2) To verify the prompt and accurate recording of all monitored data points and prompt reporting of all SAEs;
- 3) To compare CRIMSON data abstracts with individual subject records and source documents (subject charts, laboratory analyses and test results, physicians' progress notes, nurses' notes, and any other relevant original subject information);
- 4) To help ensure Investigators are in compliance with the protocol. The monitors also will inspect the clinical site regulatory files to ensure that regulatory requirements (Office for Human Research Protections-OHRP), FDA, and applicable guidelines (ICH-GCP) are being followed. During the monitoring visits, the Investigator (and/or designee) and other study personnel will be available to discuss the study progress and findings of the monitoring visit.

A specific protocol monitoring plan will be discussed with the PI and study staff prior to enrollment. The plan will outline the frequency of monitoring visits based on such factors as study enrollment, data collection status and regulatory obligations.

12.2 Data and Safety Monitoring

12.2.1 Investigator Safety Monitoring

The Investigator or designee may interrupt the administration of study drug to an individual subject, or enrollment into this study if indicated for unanticipated problems or AEs. In addition, the Investigators are responsible for:

- Protecting the safety and welfare of subjects
- Evaluating subject safety, including physician assessment of AEs for seriousness, severity, and causality
- Notifying the sponsor of SAEs and immediately-reportable events
- Providing detailed written reports, including confirmatory tests promptly following immediate initial reports
- Informing the IRB/IEC of SAEs
- Notifying the DSMB of SAEs

12.3 Safety Review and Communications Plan (SRCP)

A Safety Review and Communication Plan (SRCP) has been developed for the protocol. The SRCP is an internal communications document between the PI and the IND Sponsor Clinical Safety Office (CSO), which delineates the safety oversight responsibilities of the PI, the CSO, and other stakeholders. The SRCP also includes the overall plan for conducting periodic safety surveillance assessments.

12.4 Sponsor Medical Monitor

A Medical Monitor representing the IND Sponsor (OCRPRO) has been appointed for oversight of safety in this clinical study. The Sponsor Medical Monitor will be responsible for performing safety assessments as outlined in a Safety Review and Communications Plan (SRCP).

12.5 Data and Safety Monitoring Board DSMB

The NIAID Intramural DSMB includes independent experts that do not have direct involvement in the conduct of the study and have no significant conflicts of interests as defined by NIAID policy. The Board will review the study prior to initiation and twice a year thereafter. The Board may convene additional reviews as necessary. The Board will review the study data to evaluate the safety, efficacy, study progress, and conduct of the study. All SAEs, all UPs, and all IND Safety Reports will be reported by the PI to the DSMB at the same time they are submitted to the IRB or IND Sponsor. The PI will notify the DSMB of any cases of intentional or unintentional unblinding as soon as possible. The PI will notify the Board at the time pausing or halting criteria are met and obtain a recommendation concerning continuation, modification, or termination of the study. The PI will submit the written DSMB summary reports with recommendations to the IRB(s).

12.6 Treatment Interruption or Discontinuation

A subject's study drug infusion may be discontinued at any time at the subject's request or at the discretion of the Investigator or the Sponsor. The following may be justifiable reasons for the Investigator to discontinue a subject from SAB-301 infusion:

- The subject was erroneously included in the study (i.e., was found to not have met the eligibility criteria)
- The subject experiences an intolerable AE
- The subject is unable to comply with the requirements of the protocol
- The subject participates in another investigational study without the prior written authorization of the Sponsor

The criteria for slowing or stopping a given infusion is discussed in Section 5.3

12.7 Pausing Rules

If any of the following criteria are met at any time the study will be paused to further enrollment until assessed by the medical monitor:

- Any SAE as defined in Section 11.3 that can be possibly, probably, or definitively attributed to the study drug
- Three or more subjects in the same cohort experiencing the same Grade 2 or higher adverse effect that can be possibly, probably, or definitively attributed to the study drug
- Two or more subjects develop the same or clinically similar Grade 3 AE or laboratory abnormality
- Two or more subjects develop a serum creatinine \geq Grade 2 toxicity (≥ 1.8 mg/dL)
- Two or more subjects develop ≥ 1.5 -fold increase in serum creatinine level from baseline
- Two or more subjects develop GFR < 70 mL/min, irrespective if serum creatinine is normal range or Grade 1
- Two or more subjects develop a serum creatinine \geq Grade 2 toxicity in PT and/or PTT (i.e. one grade 2 PT and one grade 2 PTT would meet this pausing rule)

The medical monitor can request information needed (such as a listing of graded AEs and unblinded randomization scheme (directly from the NIH Clinical Center investigational pharmacy group) to evaluate the data. The sponsor medical monitor will ultimately make the decision to either resume the study, ask for formal DSMB review, or stop the study.

If the trial is stopped due to unacceptable adverse events or stopping criteria, the IRB will be notified.

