3.2 Study Design

This safety and tolerability study of intravenous (IV) SAB-301 consists of up to 6 single dose-levels or cohorts (cohort 1–6) in a double-blind, randomized, placebo-controlled dose-escalating cohort design. Six cohorts of 3-10 subjects each will be administered a single IV dose of SAB-301 or saline placebo. At very low doses, the concern is primary allergic or T-cell activation/cytokine storm, so small cohort sizes can be utilized. As the target dose is approached, the sample size will increase to increase the likelihood of detecting toxicity events. The cohorts and dose levels are outlined in [Table 1](#).

Table 1: Cohorts and Dose Levels

Cohort	Number of Subjects receiving SAB-301						Number of Subjects receiving Saline Control			
	1.0 mg/kg	2.5 mg/kg	5 mg/kg	10 mg/kg	20 mg/kg	50 mg/kg				
1	2						1			
2		2						1		
3			4						2	
4				4					2	
5					8					2
6						8				2

The administration of the study drug will occur in the day-hospital at the NIH Clinical Center. The number of subjects dosed will follow the limitations below:

- For the first cohort, no more than 1 subject will be dosed on each day.
- For the second cohort, no more than 2 subjects will be dosed on each day.
- For cohort 3-4, no more than 3 subjects will be dosed on each day.
- For cohort 5-6, no more than 3 subjects will be dosed on each day and no more than 6 subjects will be dosed per week.

Beginning with a low single-dose, subjects are randomized to receive either SAB-301 or placebo on Day 0. Subjects are then evaluated on Study Days 1, 3, 7, 21, 42, and 90.

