4.7 Discontinuation of Subject by Investigator

The Investigator has the right to withdraw subjects from the study. Subjects may be withdrawn from the study for any of the following reasons:

- The subject is lost to follow-up.
- The Investigator believes that continuation in the study would be detrimental to the subject. In general, subjects withdrawn for AEs will still be followed for safety follow-up if possible.
- If, in the Investigator's best judgment, discontinuation is in the subject's best interest.

The reason for withdrawal from the study is to be recorded in the study record. If a non-serious AE is unresolved at the time of discontinuation, efforts should be made to follow up until the event resolves or stabilizes, the subject is lost to follow-up, or there is some other resolution of the event. The Investigator should make every attempt to follow all SAEs to resolution.

Subjects withdrawn from the study after study drug administration will not be replaced.

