12.8 Dose Escalation Rules

When the results from the Day 7 visit for the last subject in a cohort (e.g., Cohort 1) are available safety parameters will be analyzed to determine the overall safety of that dose-level (e.g., 1 mg/kg). If any of the following criteria are met, the corresponding dose-level is not considered “acceptably safe”, and the study will not proceed to the next higher dose group (as the review is blinded, this will be across treatment arms).

- Any SAE that can be possibly, probably, or definitively attributed to the study drug
- Any immediate hypersensitivity or cytokine storm events
- Two or more subjects with asymptomatic positive anti-IgG (rheumatoid factor)
- One or more subjects with positive anti-IgG (rheumatoid factor) with associated rheumatologic symptoms (i.e. arthralgia, myalgia, etc.)

- Two or more subjects across all cohorts experience the same Grade 3 or higher adverse effect that can be possibly, probably, or definitively attributed to the study drug
- Three of the first 10 subjects (30%) experience the same grade 2 or higher adverse effect that can be possibly, probably, or definitively attributed to the study drug or any time thereafter 30% of enrolled subjects have the same grade 2 or higher ‘related’ AE.
- Two or more subjects across cohorts develop a serum creatinine \geq Grade 2 toxicity (≥ 1.8 mg/dL) or doubled from baseline (whichever is lower)

If any of the above criteria are met at any time, then the DSMB will meet to evaluate unblinded study data and make a determination about continuation of the study and/or amendment of the protocol.

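### The general Grade 2 pausing rule in section 12.7 cannot be met by the two SAB-301 recipients of cohort 1 or 2 alone: a narrow, low-probability gap that one sentence would close

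*Combined protocol and SAP*

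**What the plan says.** Section 12.7 stops further enrollment until the medical monitor has assessed the case if any listed criterion is met. The general one is "Three or more subjects in the same cohort experiencing the same Grade 2 or higher adverse effect", with attribution to study drug at least possible. Table 1 (section 3.2) allots two SAB-301 recipients and one saline subject to each of cohorts 1 and 2, four and two to cohorts 3 and 4, and eight and two to cohorts 5 and 6. Cohorts do not refill after dosing: "Subjects withdrawn from the study after study drug administration will not be replaced" (section 4.7; section 4.6 says the same for subjects who withdraw themselves).

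Section 3.2 explains the small first cohorts: "At very low doses, the concern is primary allergic or T-cell activation/cytokine storm, so small cohort sizes can be utilized". Section 12.8 matches that rationale, because a single occurrence blocks escalation: "Any immediate hypersensitivity or cytokine storm events". For other Grade 2 effects judged related, 12.8 counts across cohorts: "Three of the first 10 subjects (30%) experience the same grade 2 or higher adverse effect", then 30% of enrolled subjects thereafter. Counts pool both arms: "as the review is blinded, this will be across treatment arms".

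**The concern.** A fixed count of three does not scale with cohort size. It means 3 of 3 subjects in cohorts 1 and 2, 3 of 6 in cohorts 3 and 4, and 3 of 10 in cohorts 5 and 6. The rule is hardest to meet at the first doses of a first-in-human product. If every treated subject at 1 mg/kg had the same related Grade 2 effect, the rule would still be unmet unless the saline subject had it too.

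At stake is one dose step (1 to 2.5 mg/kg, or 2.5 to 5 mg/kg) taken after both recipients shared an effect, with no numeric criterion in 12.7 or 12.8 prompting an assessment first.

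**Working it through.** **Which events fall through**

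| Event in both recipients of cohort 1 or 2 | Numeric rule that applies |
|---|---|
| Related SAE | 12.7 and 12.8, one case |
| Immediate hypersensitivity or cytokine storm | 12.8, one case |
| Positive rheumatoid factor | 12.8, one case with symptoms or two without |
| Same Grade 3 event | 12.7 and (if related) 12.8, two cases |
| Grade 2 creatinine | 12.7 and 12.8, two cases |
| GFR below 70 mL/min, or Grade 2 PT/PTT | 12.7, two cases |
| Any other same, related, non-serious Grade 2 effect | none at two cases |
| Same related effect, one Grade 2 and one Grade 3 | none, because the Grade 3 rules need two Grade 3 cases |

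The last two rows are the gap. For cohort 2 it also requires no earlier case, since a third case among the first 10 subjects meets the 12.8 rule.

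**Inputs**
- Two recipients and one saline subject per cohort (Table 1).
- p = rate of the same related Grade 2 or higher effect in recipients. The documents do not give it. I use 0.20, the ceiling that section 12.9.1 sets for any Grade 2 AE, and 0.09, the any-grade headache rate of the horse botulism antitoxin cited in the risk section.
- q = rate in saline subjects. This is also not given. I assume 5–20% with p = 0.20, and 0–9% with p = 0.09.
- Subjects are independent.

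**Reproducing Table 5.** For N = 2 at a 20% rate, at least one case is 1 − 0.8² = 0.36 and two cases is 0.2² = 0.04. Both match.

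**Current rule in cohort 1 or 2.** Recipients alone: 0 at any p. With the saline subject: p²q = 0.04 × 0.05 = 0.002 to 0.04 × 0.20 = 0.008.

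**Gap in cohort 1**, p²(1 − q):
- p = 0.20: 0.04 × 0.95 = 0.038 to 0.04 × 0.80 = 0.032
- p = 0.09: 0.0081 (q = 0) to 0.0081 × 0.91 = 0.0074 (q = 9%)

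**Gap in cohort 2, no earlier case**
- Cohort 1 recipients assumed unaffected, p²(1 − q)²: 0.036 to 0.026 at p = 0.20; 0.0081 to 0.0067 at p = 0.09.
- Same p at both doses, p²(1 − p)²(1 − q)²: 0.04 × 0.64 × 0.9025 = 0.023 to 0.04 × 0.64 × 0.64 = 0.016 at p = 0.20; 0.0067 to 0.0056 at p = 0.09.

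All of these are upper bounds: two Grade 3 cases meet another rule, and 20% is a ceiling for any Grade 2 event, not for one specific related effect.

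**How soon 12.8 catches up after two cases in cohort 1** (p = 0.20, q = 5–20%)
- A third case within cohort 2: 1 − (1 − p)²(1 − q) = 1 − 0.64 × 0.95 = 0.39 to 1 − 0.64 × 0.80 = 0.49.
- A third case within the first 10 subjects (cohort 2 plus four of cohort 3, drawn at random from its four recipients and two saline subjects): 0.69 to 0.79.

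**Two-subject threshold in cohorts 1 and 2**, p² + 2p(1 − p)q:
- p = 0.20: 0.04 + 0.32 × 0.05 = 0.056 to 0.04 + 0.32 × 0.20 = 0.104 per cohort. Over both cohorts: 1 − 0.944² = 0.11 to 1 − 0.896² = 0.20.
- p = 0.09: 0.008 (q = 0) to 0.023 (q = 9%) per cohort.
- At p = 0.20, the part due to one recipient plus the saline subject, 2p(1 − p)q, is 0.016 of 0.056, or 0.064 of 0.104. The current rule already supplies 0.002 to 0.008, so the net increase is 0.054 to 0.096.

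**The case against.** The design is coherent. The protocol names allergic and cytokine reactions as the low-dose concern, acts on a single such event, and lets less specific Grade 2 effects accumulate across cohorts. That explains the small cohorts and the strict acute-reaction rule. It does not explain a general Grade 2 rule that the treated subjects cannot meet by themselves.

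A reader might go further and infer that nothing in writing requires anyone to look at such a pair before escalation. The documents do not support that:
- Section 12.8 calls for an overall safety determination once Day 7 results are in. The listed criteria force a stop, but nothing says that meeting none of them obliges escalation.
- Section 12.2.1 lets the investigator interrupt enrollment for AEs.
- Under sections 11.3, 11.4.3 and 12.5, a related event that is unexpected and raises risk is an Unanticipated Problem even if non-serious, and is reported to the sponsor's safety office and the DSMB. Whether a Grade 2 pair qualifies is a judgment.
- Section 12.4 makes the medical monitor responsible for safety assessments under the Safety Review and Communications Plan, and the précis links the monitor to escalation. That plan is not among these documents and may already require review at each step.

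A reader might also infer that such pairs are likely. The comparator does not show it. Its listed rates (headache 9%; pruritus, nausea and urticaria 5% each) are not split by grade, pruritus and urticaria may fall under the hypersensitivity rule, and the only events specifically labelled moderate are two acute allergic reactions.

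The remedy also has a real cost: with p = q = 0.20, pauses from one recipient plus the saline subject (0.064) outnumber the cohort 1 gap cases (0.032).

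**Conclusion.** The structural point is exact and depends on no assumed rate: in cohorts 1 and 2 the general Grade 2 pausing rule cannot be met without the saline subject. The practical gap is narrow. It covers a same, related, non-serious Grade 2 pair outside the specific rules, or a Grade 2 plus Grade 3 pair, in both recipients of cohort 1, or of cohort 2 with no earlier case.

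Its probability is at most about 0.03–0.04 per cohort at the protocol's ceiling and under 0.01 at 9%, given independence and the assumed saline rates. It reaches 0.20–0.24 in cohort 1 only at p = 0.5 (0.25 × 0.80 to 0.25 × 0.95), a rate with no basis in the documents. After a cohort 1 pair, 12.8 usually catches up within the first 10 subjects, though often not before one further dose step.

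The conclusion is limited to the absence of a numeric criterion in 12.7 or 12.8. Whether another document guarantees review cannot be told from here. Minor.

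**What to change.** In section 12.7 only, set the threshold for the same related Grade 2 or higher effect at two or more subjects in cohorts 1 and 2, and keep three or more in cohorts 3 to 6. Count subjects, not SAB-301 recipients, so that the rule works under blinding.

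The price is one sentence and an occasional reversible pause, with the per-cohort probabilities shown above (about 0.06–0.10 at 20%, 0.01–0.02 at 9%). Each pause also involves the DSMB under section 12.5: "The PI will notify the Board at the time pausing or halting criteria are met and obtain a recommendation concerning continuation". The medical monitor can separate a recipient pair from a recipient plus saline pair, since 12.7 provides: "The medical monitor can request information needed (such as a listing of graded AEs and unblinded randomization scheme". This may reveal the allocation of a three-person cohort to the monitor, but need not unblind the study team.

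Do not add the same threshold to 12.8. There the count is blinded, and a met criterion blocks escalation and calls a DSMB meeting on unblinded data, which is too heavy a response to pairs that may include the saline subject.
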